1.3 Safety

Risks

Activities involved with this study will involve no more than a minor increase over minimal risk. There are no alternatives to these data collection procedures. Participants may choose to not participate in any part of this voluntary study. Medical treatment (e.g. medication management) as received as part of routine clinical care will bear no more risk than usual care given the treatment will take place in the same clinical context.

Cognitive Behavioral Therapy phone sessions: **The risks of CBT are minimal.** It is possible that some of the participants may become fatigued during the treatment sessions or find it uncomfortable to talk about their situation with the therapist. Further, given the frequency with which fatigue is associated with psychological distress, as well as the inclusion of people with depression, we anticipate that some of the study participants will exhibit signs of psychological distress during treatment.

The use of telephone sessions will help to reduce the risks related to fatigue. Clinicians will be trained to be attentive to signs of fatigue or distress among all participants, who will be told they can stop any study procedures at any time if they feel uncomfortable. A participant will be referred to a medical professional if a study team member concludes they need attention regarding an acute medical issue as identified in the medical evaluation. All participants will be informed they can stop participation at any time without penalty or any effect on the medical care or benefits they receive at their MS Center (either UM Medical Center or UW Medicine MS Center), or any other medical institution. All participants will be offered the opportunity to discuss any situations or experiences associated with the study procedures they deem uncomfortable or adverse with one of the Principal Investigators or, for UW participants, the UW Site PI or Co-Investigator.

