Modafinil: Use of modafinil involves a minor increase over minimal risk. Modafinil is generally considered to be safe and well tolerated. The most common adverse reactions (5%) associated with modafinil which occurred more frequently than placebo-treated patients in previous clinical trials were headache, nausea, nervousness, rhinitis, diarrhea, back pain, anxiety, insomnia, dizziness, and dyspepsia. It is recommended that caution be used in patients with a history of psychosis, depression, or mania, to avoid exacerbation of these conditions. Serious rash requiring hospitalization and discontinuation of treatment has rarely been reported. Life-threatening skin conditions such as Steven-Johnson Syndrome or Toxic Epidermal Necrosis Syndrome, angioedema, anaphylaxis, hypersensitivity reactions involving multiple organs, new or increased psychiatric symptoms (including worsening depression, mania, depression, suicidality), or increased blood pressure are possible. Dose reduction is recommended in patients with severe hepatic impairment. Modafinil use may decrease the effectiveness of hormonal contraception, use of alternative or concomitant methods of contraception while taking modafinil and for one month after discontinuation of modafinil treatment is recommended. Elimination of drugs that are substrates for CYP2C19 (e.g., phenytoin, diazepam, propranolol, omeprazole, and clomipramine) may be prolonged by modafinil via inhibition of metabolic enzymes, with resultant higher systemic exposure.

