All potential risks of modafinil will be outlined in the informed consent document and discussed with the patient prior to enrollment. Patients will also be advised that there may be unforeseen risks not outlined in the ICF. Based on the package insert, eligibility criteria will exclude pregnant women, and a urine pregnancy test will be required prior to study enrollment. Women of childbearing age will be advised of the risk of decreased effectiveness of hormonal contraception with modafinil use and be advised to use a form of birth control that does not involve hormonal contraception (spermicide or condoms) during the study and for one month after discontinuation of modafinil treatment. Participants with a history of hepatic impairment, participants over age 65, and participants who use warfarin, phenytoin, MAOIs and cyclosporine will be given dose limitations that will not exceed half of the maximal daily dose for healthy patients (50-100 mg once-twice daily as tolerated). Patients will be advised to monitor for common side effects of modafinil including headache, nausea, nervousness, rhinitis, diarrhea, back pain, anxiety, insomnia, dizziness, and dyspepsia while on modafinil, and if these symptoms occur or worsen, to alert the study team, during which time dose reduction or discontinuation will be discussed. Participants who experience worsening depressive symptoms, psychosis, increased suicidality, or suspected allergic reactions (rash, hives, mouth sores, blisters, swelling of the face, eyes, lips, tongue, or throat, trouble swallowing or breathing, fever, shortness of breath, swelling of the legs, yellowing of the skin or whites of the eyes, or dark urine) will be instructed to stop treatment immediately and contact the study team. Participants are also advised not to consume alcohol per the drug label. Participants should be instructed to call study team when new drugs are added or removed from their drug regimens so that drug interactions can be assessed. Participants may choose to discontinue their treatment at any time if they experience any untoward effects that they believe are related to modafinil, but will be encouraged to remain in the study until completion for monitoring. Adverse events and severe adverse events will be assessed/reported regularly and on an as-needed basis in accordance with the protocol, GCP, and IRB standards (see sections 7.5 and 8). Action involving possible PI discontinuation of study drug will be determined promptly in accordance with the protocol, GCP and IRB guidelines, as well as the medical monitor (see section 10 and 13).

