7.5 Adverse Event Assessments

Adverse events that are NOT related to the normal course or chronic symptoms of MS (such as relapses, MRI progression, somatic pain, weakness, numbness, visual disturbances, bladder/bowel symptoms) or events that are expected to occur in the course of daily life or use of disease modifying therapy (injuries, infections, disease modifying therapy infusion reactions, disease modifying therapy injection site reactions, disease modifying therapy-induced lymphopenia) **will be assessed/collected at each visit, scheduled phone call, or unscheduled phone call.**

Participants will be queried about any symptoms they have been experiencing while on the study, with directed questions toward adverse outcomes previously reported with the study treatments (including headache, nausea, nervousness, rhinitis, diarrhea, anxiety, insomnia, dizziness, dyspepsia, worsening depressive symptoms, psychosis, increased suicidality) or suspected allergic reactions: rash, hives, mouth sores, blisters, swelling of your face, eyes, lips, tongue, or throat, trouble swallowing or breathing, fever, shortness of breath, swelling of the legs, yellowing of the skin or whites of the eyes, or dark urine.

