Aim 3: Compare adverse events, side effects, treatment adherence, and patient dropout rates among the three treatment arms and patient subgroups of interest. Descriptive statistics will be used to analyze patterns of adverse events including side effects (incidence, type, severity, and relatedness) and treatment adherence between treatment groups (modafinil vs. CBT vs. combination therapy) throughout the 12-week intervention interval. Adverse event frequency between treatment groups and among subgroups of interest will be evaluated using ANOVA. Multiple linear regression models adjusted for age, gender, EDSS score, baseline fatigue level, baseline activity level, presence of sleep disorder (yes/no), and depression severity (PHQ-8 Score) will be used to determine association between treatment group and treatment adherence (percent usage of prescribed therapy). We also will assess whether degree of treatment effects measured in Aim 1 are related to treatment adherence (e.g. “dose response”).

9.3 Analysis of Exploratory Aims:

Additional analyses modeled as in 9.2 above will also evaluate treatment effect on the difference between 8 week and baseline MFIS scores, to assess whether treatment effects are detectable prior to the 12-week assessment period.

Additional analyses modeled as in 9.2 above will also evaluate treatment effect on the difference between 24 week and baseline MFIS scores, to assess whether treatment effects are detectable following the 12-week assessment period.

Descriptive statistics will be used to summarize clinical treatment utilization patterns between 12-24 weeks, following the 12-week intervention interval.

Analyses modeled as in 9.2 will also be used to evaluate treatment effects on other outcomes at 12 and 24 weeks. We will examine differential treatment effects on changes in the following

factors (assessed via survey): ability to participate in social roles and activities, pain interference, quality of life, and self-efficacy for managing MS symptoms. We will also examine differential treatment effects on changes from baseline to 12 and 24 weeks in the following outcomes that were assessed via survey and/or EMA: pain intensity, perceived cognitive functioning, and pacing behaviors. Treatment group differences in scores on the PGIC measure at 12 and 24 weeks will be examined in models similar to the approach described in 9.2.

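### The directed adverse-event questions are weighted toward modafinil: two of the three CBT harms the protocol foresees have no item, and the third is only partly covered

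*Combined protocol and SAP*

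**What the plan says.** Section 7.5 describes two layers of elicitation. The first is open: "Participants will be queried about any symptoms they have been experiencing while on the study". The second is a set of prompts, "with directed questions toward adverse outcomes previously reported with the study treatments (including headache, nausea, nervousness, rhinitis, diarrhea, anxiety, insomnia, dizziness, dyspepsia", which continues with "worsening depressive symptoms, psychosis, increased suicidality) or suspected allergic reactions" and then lists the allergic signs. The text makes no distinction by arm.

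Section 1.3 sets out the CBT risks separately. It says that "some of the participants may become fatigued during the treatment sessions or find it uncomfortable to talk about their situation with the therapist", and, given the link between fatigue and distress and the inclusion of people with depression, "we anticipate that some of the study participants will exhibit signs of psychological distress during treatment".

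Under Aim 3 in section 9.2, harms are compared across the three arms: "Descriptive statistics will be used to analyze patterns of adverse events including side effects (incidence, type, severity, and relatedness") for modafinil, CBT and the combination, with adverse-event frequency tested by ANOVA.

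**The concern.** The Protocol Summary presents the trial as a comparison of benefits and harms, and Aim 3 carries the harms half. A symptom that is named to the participant is generally reported more readily than one left to an open question. If the named symptoms come from one treatment's risk profile, that treatment's harms are captured more fully.

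Two contrasts could be affected. CBT against modafinil would tend to favour CBT. Modafinil against the combination, which shows what CBT adds in harm, would tend to show too little. Events that were never elicited cannot be recovered in the analysis.

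**Working it through.** The plan has no figure to reproduce here. It states no expected adverse-event rate, and its Aim 3 power statement in section 9.1 concerns adherence. The check is a comparison of texts.

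**Step 1. Where the directed terms come from.** The common modafinil reactions in section 1.3 are "headache, nausea, nervousness, rhinitis, diarrhea, back pain, anxiety, insomnia, dizziness, and dyspepsia", which is 10 terms. All but back pain are in the 7.5 list: 10 − 1 = 9. The other three named symptoms match the modafinil stop-and-call instruction in section 1.3: "Participants who experience worsening depressive symptoms, psychosis, increased suicidality, or suspected allergic reactions". So 9 + 3 = 12 of 12 named symptoms trace to the modafinil text. The allergic signs follow the same instruction.

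**Step 2. Whether the CBT harms in section 1.3 have a directed item.**

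| CBT harm in 1.3 | Directed item in 7.5 |
|---|---|
| Fatigue during sessions | None |
| Discomfort in talking with the therapist | None |
| Psychological distress | Partial: anxiety, nervousness, worsening depression, greater suicidality |

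Two of three have no item and one of three is partly covered.

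**Step 3. Whether another route fills the gap.**
- *Open question.* It reaches all arms and is the main remaining route.
- *Surveys.* PHQ-8, GAD-7 and MFIS are collected in all arms, but section 6.6 says the survey data do not serve safety assessment.
- *Therapists.* Section 1.3 has clinicians watch for fatigue and distress. Section 6.6 gives safety assessments to the coordinator, and no path from a therapist's observation to the adverse-event record is described.
- *MS-symptom filter.* Section 7.5 leaves out events that belong to the normal course or chronic symptoms of MS. Fatigue is not among its examples. However, the Protocol Summary treats fatigue as one of the commonest MS symptoms, and section 4.1 requires at least three months of problematic fatigue at entry. Session-related fatigue could therefore be read as falling under the filter.

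**Step 4. Size.** Let p be the true proportion with a given CBT harm, d the fraction recorded when it is prompted, and q the fraction recorded from the open question alone. The shortfall is p × (d − q) per CBT recipient, and it is zero if q = d. The documents give none of p, d or q, so no number follows. With 1:1:1 allocation, two of the three arms receive CBT: 2/3 × 300 = 200 of the target completers, or 2/3 × 330 = 220 of those to be enrolled.

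**The case against.** The case on the other side has real substance.

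A reader might infer that no CBT harm is asked about and that the comparison is one-sided by design. The text does not support that. The three psychiatric terms in the second half of the 7.5 sentence, with anxiety and nervousness, are recognisable forms of psychological distress. The open question is active elicitation, not a wait for volunteered reports. The list is introduced as illustrative, it refers to the study treatments in the plural, and the same questions go to all arms. That a term comes from the modafinil text does not make it specific to the drug: anxiety or insomnia would be prompted in a CBT participant too.

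A reader might also infer that session fatigue is excluded from collection. Section 7.5 does not say so; it is only open to that reading.

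On materiality, the two harms without a prompt may be brief, and section 1.3 rates the risks of CBT as minimal. CBT recipients also have repeated therapist contact, and section 1.3 invites all participants to discuss experiences they find uncomfortable or adverse. A fatigue prompt has its own difficulty, since fatigue impact is the primary outcome and participants are unblinded.

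These points limit the severity and shape the remedy. They do not supply a prompt for the two uncovered harms, and no CBT-specific item is written anywhere in the plan.

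Groups 2 and 3 also have two extra early adverse-event reviews under section 6.9, making four scheduled reviews after treatment start through week 12 against two in Group 1. That is a separate imbalance in contact. Equalising it would not add the missing questions.

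**Conclusion.** The point holds in a limited form: prompting is weighted toward modafinil, and CBT harms may be under-counted relative to modafinil harms in Aim 3. The evidence is the count in the text: 12 of 12 named symptoms from the modafinil risk text, two of three foreseen CBT harms with no item, and one partly covered. The direction rests on the assumption that a named symptom is recorded more often than one left to an open question.

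An estimate of how many events would be missed might be tempting, but any such figure would rest on rates from outside the documents. The Aim 1 analysis is not affected. This is a cheap improvement of low severity.

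**What to change.** Add two items to the directed list in section 7.5, in identical neutral words in all three arms, at the scheduled reviews common to all arms:

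- (a) emotional distress or discomfort during the study treatment period;
- (b) transient worsening of fatigue during or shortly after a session or dose.

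Grade relatedness afterwards under section 8.1, so that the question itself does not ask for a cause. State in 7.5 that (b) is recorded and not screened out as an MS symptom. In section 9.2, report (b) separately from overall adverse-event frequency, because it lies close to the primary outcome and could otherwise count non-response or natural fluctuation as harm.

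The cost is two more questions on an existing form and a CRF update. Some overlap of (b) with the efficacy outcome will remain, and unblinded participants may still attribute symptoms to their treatment. If recruitment has begun, events collected before the change are not comparable with later ones and should be reported separately.

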8. ADVERSE EVENT REPORTING

Multiple Sclerosis is a disease with many disease-related symptoms and complications, and there are many common mild side effects associated with disease modifying therapy use. Due to the patient population and the nature of the disease, as well as the lack of experimental interventions in this study (only standard of care procedures and treatments will be used) we would like to implement the following AE/SAE collection/reporting guidelines:

SAE events that meet all 3 of the following criteria will be collected and submitted to the IRB:

- Serious;
- Related; and
- Unexpected

SAEs that are unrelated, regardless of expectedness, will not be reported to the IRB.

In addition, the following AEs will be collected and submitted to the IRB:

- Any related and unexpected AE that results in a change to research or participant's treatment plan

The medical monitor (see section 10.2) will also receive reports of all AEs collected in section 7.5, and SAEs regardless of expectedness or relatedness.

8.1 AE/SAE relatedness:

- a. *Definitely related*: clearly associated with study drug/treatment
- b. *Probably related*: likely associated with study drug/treatment
- c. *Possibly related*: may be associated with study drug or other treatment
- d. *Unlikely to be related*, or
- e. *Definitely not related* to the study drug/treatment

For reporting purposes, an AE should be regarded as definitely or probably related to the regimen if the investigator believes that at least one of following criteria are met:

- a. There is a clinically plausible time sequence between onset of the AE and the administration of the study drug or treatment.
- b. There is a biologically plausible mechanism for the study drug or treatment causing or contributing to the AE.
- c. The AE cannot be attributed solely to concurrent/underlying illness, other drugs, or procedures.
- d. A potential alternative cause does not exist.

8.2. Serious Adverse Events (SAE) Definition: An adverse drug experience occurring at any dose that results in any of the following outcomes:

- a. Death
- b. A life-threatening adverse drug experience

- c. Inpatient hospitalization or prolongation of existing hospitalization
- d. A persistent or significant disability &/or incapacity
- e. A congenital anomaly or birth defect

Important medical events that may not result in death, be life-threatening, or require hospitalization may be considered a serious adverse drug experience when, based upon appropriate medical judgment, they may jeopardize the patient or subject and may require medical or surgical intervention to prevent one of the outcomes listed in this definition. A serious adverse experience includes any experience that is fatal or immediately life threatening, results in a persistent or significant disability/incapacity, requires or prolongs in-patient hospitalization, or is a congenital anomaly, cancer, or overdose.

Other important medical events that may not result in death, not be life-threatening, or not require hospitalization may be considered a serious adverse experience when, based upon appropriate medical judgment, the event may jeopardize the subject/patient and may require medical or surgical intervention to prevent one of the outcomes listed previously.

8.3 AE/SAE Expectedness:

Expected adverse events are those adverse events that are listed in the protocol, the Investigator's Brochure (current edition) or in the study informed consent document.

Unexpected adverse events are those that:

- a. are not described in the Investigator's Brochure, approved label, or the clinical protocol as far as the study drug is concerned.
- b. are not anticipated in the study informed consent. This includes adverse events for which the specificity or severity is not consistent with the description in the informed consent.

Unanticipated problem: Per FDA Procedural Guidance for Clinical Investigators, Sponsors, and IRBs (January 2009), a serious problem that has implications for the conduct of the study (requiring a significant and usually safety-related, change in the protocol such as revising inclusion/exclusion criteria or including a new monitoring requirement, informed consent or investigator's brochure).

Unanticipated problem Reporting: Per 21 CFR 312.66, 312.53 (c)(1)(vii), and 56.108(b)(1), should an Unanticipated problem occur during the investigation, the investigator will promptly report all unanticipated problems involving risks to human subjects or others to IRBMED and FDA according to the reporting requirements and guidelines.

8.4 AE/SAE severity: *The severity or grade of an adverse event may be measured using the following definitions:*

Mild: Noticeable to the subject, but does not interfere with subject's expected daily activities, usually does not require additional therapy or intervention, dose reduction, or discontinuation of the study.

Moderate: Interferes with the subject's expected daily activities, may require some additional therapy or intervention but does not require discontinuation of the study.

Severe: Extremely limits the subject's daily activities and may require discontinuation of study therapy, and/or additional treatment or intervention to resolve.

9.0 DATA ANALYSIS/STATISTICAL METHODS

9.1 Sample Size Determination

Estimates are derived from recent data from the study team, and published interventional studies of modafinil and CBT monotherapy. The primary sample size determinant for this study is Aim 1.

For Aim 1, we have chosen the Modified Fatigue Impact Score (MFIS) as the primary outcome variable of interest. The MFIS has been validated in MS patients, is frequently used in MS clinical studies as a reliable measure of fatigue, and is sensitive to changes in intervention. The primary outcome measure will be the mean within-subject difference between baseline and 12-week MFIS values (delta-MFIS), compared between groups. Based on a power analysis of 2-sample means (combined monotherapy groups vs. combination therapy, group weights 2:1), with a 2-sided alpha of 0.05 and standard deviation of 12, a sample size of n=300 subjects will provide 92% power to detect a delta-MFIS of 5 between the monotherapy and combination treatment arms (see power curve); this difference is similar to group differences found in previous fatigue trials.

For Aim 2 analyses, using fatigue outcomes as the dependent variables (in separate models) a multiple linear regression power analysis was performed assuming a full model consisting of up to 11 possible predictor variables: treatment group, presence of sleep disturbance (yes/no), depression severity (PHQ-9 Score), disability severity (EDSS score), 3 interaction terms (treatment*sleep, treatment*depression, and treatment*disability), baseline fatigue level, anxiety, pain, and exercise. A similar model will also be constructed using MS subtype and treatment*MS subtype interaction term, (in place of EDSS) to determine if subtype conveys differences in fatigue outcome separate from pure disability measures. Based on a sample size of n=300, we will have 85% power to detect an R-square difference of 0.04 for the interaction term of interest, assuming the R-squared explained by the adjustment variables is at least 0.3.

For Aim 3, using treatment adherence as the dependent variable (continuous outcome), a multiple linear regression power analysis was performed assuming a full model consisting of up to 8 possible predictor variables: treatment group (independent variable of interest), age, gender, EDSS score, baseline fatigue level, baseline activity level, presence of sleep disturbance (yes/no), and depression severity (PHQ-9 Score). Based on a sample size of n=300, we will have 95% power to detect an R-square difference of 0.03 for the test predictor of interest, assuming the R-squared explained by the adjustment variables is at least 0.3.

9.2 Analysis of Study Aims:

Aim 1: Compare the effectiveness of 3 therapies: CBT monotherapy, modafinil monotherapy, and CBT+modafinil combination therapy on patient-reported fatigue impact (primary outcome), fatigue intensity, and fatigability among fatigued individuals with MS. The primary outcome measure will be the mean difference in Modified Fatigue Impact Scale (MFIS) score between 12 weeks and baseline (delta-MFIS), compared between treatment groups. A repeated measures mixed effects model will be applied. The mean difference will also be adjusted for baseline covariates: age, gender, anxiety, pain, and exercise, which were included as covariates based on their established association between fatigue and/or activity in MS. Additional secondary analyses will also evaluate treatment effect on EMA outcome measures of fatigue impact, fatigue intensity, and fatigability.

Aim 2: Test whether depression, sleep disturbances, or MS disability level modify comparative treatment responsiveness across treatment arms in terms of fatigue impact (HTE analyses). Treatment group effect on fatigue impact scores, fatigue intensity, and fatigability among select subgroups, including those with clinically significant depression, progressive MS subtype and higher EDSS scores, and confirmed/suspected sleep disorders not related to poor sleep hygiene, will be evaluated with interaction terms in mixed effects models as above.

Aim 3: Compare adverse events, side effects, treatment adherence, and patient dropout rates among the three treatment arms and patient subgroups of interest. Descriptive statistics will be used to analyze patterns of adverse events including side effects (incidence, type, severity, and relatedness) and treatment adherence between treatment groups (modafinil vs. CBT vs. combination therapy) throughout the 12-week intervention interval. Adverse event frequency between treatment groups and among subgroups of interest will be evaluated using ANOVA. Multiple linear regression models adjusted for age, gender, EDSS score, baseline fatigue level, baseline activity level, presence of sleep disorder (yes/no), and depression severity (PHQ-8 Score) will be used to determine association between treatment group and treatment adherence (percent usage of prescribed therapy). We also will assess whether degree of treatment effects measured in Aim 1 are related to treatment adherence (e.g. “dose response”).

9.3 Analysis of Exploratory Aims:

Additional analyses modeled as in 9.2 above will also evaluate treatment effect on the difference between 8 week and baseline MFIS scores, to assess whether treatment effects are detectable prior to the 12-week assessment period.

Additional analyses modeled as in 9.2 above will also evaluate treatment effect on the difference between 24 week and baseline MFIS scores, to assess whether treatment effects are detectable following the 12-week assessment period.

Descriptive statistics will be used to summarize clinical treatment utilization patterns between 12-24 weeks, following the 12-week intervention interval.

Analyses modeled as in 9.2 will also be used to evaluate treatment effects on other outcomes at 12 and 24 weeks. We will examine differential treatment effects on changes in the following

factors (assessed via survey): ability to participate in social roles and activities, pain interference, quality of life, and self-efficacy for managing MS symptoms. We will also examine differential treatment effects on changes from baseline to 12 and 24 weeks in the following outcomes that were assessed via survey and/or EMA: pain intensity, perceived cognitive functioning, and pacing behaviors. Treatment group differences in scores on the PGIC measure at 12 and 24 weeks will be examined in models similar to the approach described in 9.2.

If potential mediators of the treatment effects, such as self-efficacy for managing symptoms, sleep, depressed mood, and anxiety, show significant changes from baseline to 8 weeks, mediational analyses, either structural equation modeling or mixed effects regression models will be used to test whether the effects of the treatment arms are mediated through common (simple mediational analyses) or different (moderated mediation) mechanisms.

